8.8 Safety Analysis

Safety will be analyzed for the FAS.

8.8.1 Adverse Events

All reported AEs will be listed from the start of dosing with sebelipase alfa to the end of participation in this study. Separate listings of SAEs and IARs will also be provided. The numbers and percentages of subjects experiencing any AE, any SAE, any IAR, any related AE, any related SAE, and discontinuations due to an AE will be tabulated.

The frequency of treatment-emergent AEs, SAEs, and IARs by system organ class SOC and preferred term (coded using Medical Dictionary for Regulatory Activities [MedDRA[®]] version 14 or higher) will be tabulated. Frequencies will also be presented by the classifications of severity and causality. In addition, frequency of AEs, SAEs, and IARs will be presented for time periods spanning the entire course of treatment with sebelipase alfa: from the start of dosing with sebelipase alfa in this study to 3 months after the first dose, >3 to 6 months, >6 to 12 months, >12 to 18 months, >18 to 24 months and >24 months. As appropriate, additional listings, summary tables and graphics will be generated to evaluate IAR frequency and severity over time. A listing of subjects who withdraw from the study due to AEs will be presented, and the incidence of AEs leading to study discontinuation will be summarized.

8.8.2 Clinical Laboratory Tests

Observed measurements and changes from baseline to each study timepoint in clinical laboratory data will be summarized. Clinically significant abnormal values will be listed. Frequencies of abnormal values relative to the laboratory normal range and clinically significant abnormal values will be tabulated for each study timepoint. Shift tables may also be provided.

The percentage of subjects who become ADA positive, time to ADA positivity, median and peak IgG antibody titer, time to peak IgG antibody titer, and percentage of subjects who tolerize will be summarized; IgG antibody titer values will be tabulated at each study visit using summary statistics appropriate to the data.

8.8.3 Other Safety Data

Changes in vital signs from pre-infusion values to each time point during or post-infusion will be summarized. Abnormal findings/values for physical examinations, vital signs, and ECGs will also be listed.

Concomitant medication/treatment data will be coded using the WHO-DRUG dictionary. All data will be listed, and the percentages of subjects receiving each concomitant medication/treatment will be tabulated.

8.9 Pharmacokinetics

Pharmacokinetics will be analyzed for the PK Analysis Set. C_{max} will be recorded from direct observation, and CL will be derived by non-compartmental analysis. PK parameters will be summarized by dose of sebelipase alfa, if applicable.

8.10 Pharmacodynamic Analysis

Potential disease-related biomarkers will be listed, and observed values and changes and/or percent changes from baseline will be summarized at available timepoints.

8.11 Other Statistical Issues

8.11.1 Significance Levels

No formal hypothesis tests are planned. P-values, where presented, will be based on a 2-sided alpha of 0.05 and are intended to guide clinical judgment and interpretation of the data.

8.12 Subgroup Analyses

The impact of ADAs on safety, efficacy, PK, and PD endpoints will be explored descriptively. As subject numbers permit, other subgroup analyses of interest may be performed. These may include, but are not limited to age, gender, and race.

8.13 Missing or Invalid Data

All data will be analyzed as they were collected in the database.

Page 60 of 76

8.14 Interim Analysis

No interim analyses are planned.

9 Data Handling and Record Keeping

9.1 Confidentiality

Information about study subjects will be kept confidential and managed according to the requirements of applicable local regulations.

9.2 Source Documents

Source data is all information, original records of clinical findings, observations, or other activities in a clinical trial necessary for the reconstruction and evaluation of the trial. Source data are contained in source documents. Examples of these original documents, and data records include: hospital records, clinical and office charts, laboratory notes, memoranda, subjects' diaries or evaluation checklists, pharmacy dispensing records, recorded data from automated instruments, copies or transcriptions certified after verification as being accurate and complete, microfiches, photographic negatives, microfilm or magnetic media, x-rays, subject files, and records kept at the pharmacy, at the laboratories, and at medico-technical departments involved in the clinical trial.

9.3 Case Report Forms

Required data for this study will be captured on eCRFs via electronic data capture unless otherwise specified in this document. Except for data points for which the protocol indicates that the eCRF may serve as source documentation, data are to be obtained from the subject's source documents and then entered into the eCRF by authorized site personnel. Clinical data that are not recorded on the eCRF will be captured and transferred to the Sponsor or its designee.

9.4 Records Retention

It is the Investigator's responsibility to retain study essential documents for at least 2 years after the last approval of a marketing application in their country and until there are no pending or contemplated marketing applications in their country or at least 2 years have elapsed since the formal discontinuation of clinical development of the investigational product. These documents should be retained for a longer period if required by an agreement with the Sponsor. In such an instance, it is the responsibility of the Sponsor to inform the Investigator/institution as to when these documents no longer need to be retained.

10 Study Monitoring, Auditing, and Inspecting

10.1 Study Monitoring Plan

This study will be monitored according to the study monitoring plan. The Investigator will allocate adequate time for such monitoring activities. The Investigator will also ensure that the monitor or other compliance or quality assurance reviewer is given access to all the above noted study-related documents and study related facilities (e.g. pharmacy, diagnostic laboratory, etc.), and has adequate space to conduct the monitoring visit.

10.2 Auditing and Inspecting

The Investigator will permit study-related monitoring, audits, and inspections by the IRB/IEC, the Sponsor, government regulatory authorities, and quality assurance groups of all study related documents (e.g. source documents, regulatory documents, data collection instruments, study data etc.). The Investigator will ensure the capability for inspections of applicable study-related facilities (e.g., pharmacy, diagnostic laboratory, etc.).

Participation as an Investigator in this study implies acceptance of potential inspection by government regulatory authorities and applicable compliance and quality assurance offices.

Page 62 of 76

11 Ethical Considerations

This study is to be conducted according to US and international standards of GCP (FDA Title 21 part 312 and ICH guidelines), applicable government regulations and Institutional research policies and procedures.

This protocol and any amendments will be submitted to a properly constituted IRB/IEC, in agreement with local legal prescriptions, for formal approval of the study conduct. The decision of the IRB/IEC concerning the conduct of the study will be made in writing to the Investigator and a copy of this decision will be provided to the Sponsor before commencement of this study. The Investigator should provide a list of IRB/IEC members and their affiliate to the Sponsor.

Each subject's parent or legal guardian for this study will be provided a consent form describing this study and providing sufficient information for the subject's parent or legal guardian to make an informed decision about their child's participation in this study. This consent form will be submitted with the protocol for review and approval by the IRB/IEC for the study. The formal consent of a subject, using the IRB/IEC-approved consent form, must be obtained before that subject undergoes any study procedure. The consent form must be signed by the subject's parent or legal guardian, and the Investigator-designated research professional obtaining the consent.

Any changes in the study protocol, such as changes in the study design, objectives or endpoints, inclusion and exclusion criteria, and/or procedures (except to eliminate an immediate hazard) will be implemented only after the mutual agreement of the Investigator and the Sponsor or designee. All protocol changes must be documented in protocol amendment(s). Protocol amendment(s) must be signed by the Investigator and approved by the IRB/IEC prior to implementation. Any changes in study conduct that result from a pending amendment will be considered protocol deviations until IRB/IEC approval is granted. Documentation of IRB/IEC approval must be returned to the Sponsor or designee.

12 Clinical Study Report and Publication Plan

A clinical study report will be produced after all subjects have reached 12 months of age or have died or withdrawn from the study, and will include all available subject data through 12 months of age or the date of death or early withdrawal. A final clinical study report will be produced after study completion, and will include cumulative subject data for the entire period of treatment in the study. A coordinating Investigator will be designated to review and sign the completed clinical study reports.

It is intended that the results from this research will be submitted to a peer-reviewed medical publication, once the study is completed, regardless of the outcome.

Page 64 of 76

13 References

Andrews L and O'Callaghan M. Enzyme Replacement Therapies. From *Preclinical Safety Evaluation of Biopharmaceuticals: a Science-Based Approach to Facilitating Clinical Trials.* Edited by Joy A. Cavagnaro. John Wiley and Sons. 2008.

DNA Sample (parents)	Х															
PK Sample		Х											Х			
PBMC LAL Activity	Х															
DBS LAL Activity	Х															
Sebelipase alfa Dosing		Х	Х	Х	Х	Х	Х	Х	Х	Х	Х	Х	Х	Х		
Anti-drug Antibody	XP			XP				XP		XP		XP		X		
Adverse Events ²	CONTINUOUS															
Concomitant Therapies		CONTINUOUS														
	• •		-													•

* All visits will be calculated from Week 0; consecutive infusions must be administered at least 5 days apart.

P Pre-dose

1 Abdominal MRI should be considered in subjects receiving general anesthesia and/or sedation for other procedures. The MRI should be scheduled at least 3 months after the preceding MRI assessment. If an MRI cannot be performed, an Ultrasound will be performed.

Page 69 of 76

2 For the subjects who are stable enough to be treated on an outpatient basis, safety follow-up assessments for AEs will be conducted by telephone 24 hours following the first 2 infusions of 0.35 mg·kg⁻¹ qw, 1 mg·kg⁻¹ qw, and, if applicable, 3 mg·kg⁻¹ qw and 5 mg·kg⁻¹ qw.

Page 70 of 76
Appendix A: Schedule of Assessments Table 2 -- Week 25 through 156 (Year 3)*

	Week 25-Week 156													
Assessments	Every week	Week 32	Week 36	Week 40	Week 48	Week 60	Week 72	Week 84	Week 96	Week 108	Week 120	Week 132	Week 144	Week 156
		±2 days	±2 days	±2 days	±2 days	±2 days	±2 days	±2 days	±2 days	±2 days	±2 days	±2 days	±2 days	±2 days
Physical Exam			XP		XP	XP	XP	XP	XP	XP	XP	XP	XP	XP
Photographs							х				х			
Anthropometrics														
Weight	XP													
Recumbent length or height, and abdominal circumference			х		х	х	х	х	х	х	х	х	х	х
Head and mid-upper arm circumference			Х		х	х	Х	х	Х					
Vital Signs	х													
12-lead ECG							If clinically	/ indicated						
Denver II ¹							XP				XP			
Abdominal Ultrasound ¹							х				х			
Abdominal MRI ^{1,2}							Х				х			
Liver Biopsy								Optional	after at leas	st 1 year of	treatment			
Clinical LabTests ³		XP		XP	XP	XP	XP	XP	XP	XP	XP	XP	XP	XP
Exploratory Biomarkers ³					XP		XP		XP		XP		XP	
PK Sample ³							х							
Sebelipase alfa Dosing ⁴	х													
Anti-drug Antibody ³			XP		XP	XP	XP	XP	XP	XP	XP	XP	XP	XP
Adverse Events ⁵	CONTINUOUS													
Concomitant Therapies							CONTI	NUOUS						

* All visits will be calculated from Week 0; consecutive infusions must be administered at least 5 days apart.

P Pre-dose

1 Assessments can be performed (±15) days of scheduled visit.

2 Abdominal MRI should be considered in subjects receiving general anesthesia and/or sedation for other procedures. The MRI should be scheduled at least 3 months after the preceding MRI assessment. If an MRI cannot be performed, an ultrasound will be performed.

3 If blood volume is limited, refer to Section 5.1.11 for tiered assessments.

4 Subjects may transition to an every other week dosing schedule after 96 weeks if on a stable dose for at least 24 weeks.

Page 71 of 76

5 For the subjects who are stable enough to be treated on an outpatient basis, safety follow-up assessments for AEs will be conducted by telephone 24 hours following the first 2 infusions of 0.35 mg kg^{-1} qw, 1 mg kg^{-1} qw, and, if applicable, 3 mg kg^{-1} qw and 5 mg kg^{-1} qw.

	Week 157- Week 260 (
Assessments	Every week	Week 168	Week 180	Week 192	Week 204	Week 216	Week 228	Week 240	Week 252	Follow-up/ Early Withdrawal ¹		
		±2 days	± 2 days	± 7 days								
Physical Exam		XP	XP	XP	XP	XP	XP	XP	XP	Х		
Photographs		х				х						
Anthropometrics												
Weight	XP									x		
Recumbent length or height, and abdominal circumference		х	Х	Х	Х	Х	Х	Х	Х	Х		
Vital Signs	Х											
12-lead ECG		If clinically indicated										
Denver II ²		х				х				Х		
Abdominal Ultrasound ²		x x .										
Abdominal MRI ^{2,3}		х				х						
Liver Biopsy		Optional after at least 1 year of treatment										
Clinical LabTests ⁴		XP	XP	XP	XP	XP	XP	XP	XP	X		
Exploratory Biomarkers ⁴		XP		XP		XP		XP		Х		
Sebelipase alfa Dosing ⁵	х											
Anti-drug Antibody ⁴		XP	XP	XP	XP	XP	XP	XP	XP	Х		
Adverse Events ⁶		CONTINUOUS										
Concomitant Therapies	CONTINUOUS											

Appendix A: Schedule of Assessments Table 3 -- Week 157 through 260 (Year 5)*

* All visits will be calculated from Week 0; consecutive infusions must be administered at least 5 days apart.

P Pre-dose

1 The follow-up / early withdrawal visit will be conducted 30 (+7) days after the last dose of IMP.

2 Assessments can be performed (±15) days of scheduled visit.

3 Abdominal MRI should be considered in subjects receiving general anesthesia and/or sedation for other procedures. The MRI should be scheduled at least 3 months after the preceding MRI assessment. If an MRI cannot be performed, an Ultrasound will be performed.

4 If blood volume is limited, refer to Section 5.1.11 for tiered assessments.

5 Subjects may transition to an every other week dosing schedule after 96 weeks if on a stable dose for at least 24 weeks.

Page 72 of 76

05 January 2016

Page 73 of 76

Symptoms may include but are not	Actions in accordance with institutional
limited to:	standard of care
Mild Common • Hyperemia (Flushing) • Lightheadedness • Nausea • Mild chest discomfort (tightness) Less Common • Fever and/or shivering • Palpitations • Headache • Irritability (especially in young children)	 Slow infusion rate by 50% Administer oral anti-pyretic and/or antihistamine Decrease infusion rate by a further 25% if symptoms persist Increase infusion time If the event resolves, the infusion should continue at reduced rate for a minimum of 30 minutes before infusion is increased to 75% of original rate. If subject tolerates infusion at 75% of the original rate for at least 30 minutes the original rate may be restored for the remainder of the infusion. If symptoms continue despite rate reduction stop infusion Pre-treat with oral antihistamine and antipyretic prior (approximately 1.5h) to next infusion e.g., diphenhydramine (1 mg/kg po) and acetaminophen (15 mg/kg po)
 Moderate Reaction Hyperemia (flushing) Chest discomfort Itching and/or raised urticarial rash Severe headache Gastro intestinal symptoms, vomiting, diarrhoea, abdominal cramping. 	 Stop Infusion Give antihistamine IV and consider IV steroids Give any prescribed inhaler treatment if appropriate If the event has resolves, the infusion may continue at reduced rate of 50% of the original for a minimum of 30 minutes before infusion is increased to 75% of original rate. If patient tolerates infusion at 75% of the original rate for at least 30 minutes the original rate for at least 30 minutes the original rate may be restored for the remainder of the infusion. Pre-treat with oral antihistamine and antipyretic prior to next infusion Collect serum sample for tryptase 1-3 hours after the IAR onset and another serum sample for tryptase and ADA during the next study visit (≥ 4 days after the IAR) prior to the infusion. Skin testing may be considered.

Appendix B: Diagnosis and Recommendations for Management of Infusion Associated Reactions

Page 74 of 76

Severe Reaction	 Stop Infusion Give oxygen, if available 						
 Clinically significant cardiovascular effects: e.g., hypertension or hypotension defined as a decline approaching 20-30% of their preinfusion value without alternative etiology, agitation, pain, fluid overload, dehydration Respiratory symptoms: Significant shortness of breath, stridor, wheezing, laryngeal oedema, swelling of tongue. Cardiac Arrhythmias 	 Give oxygen, if available Give epinephrine (adrenaline) IM or inhaled Give antihistamines IV and steroids IV Collect serum sample for tryptase 1-3 hours after the IAR onset and another serum sample for tryptase and ADA during the next study visit (≥ 4 days after the IAR) prior to the infusion. Skin testing may be considered Dosing of the subject will be suspended until the Safety Committee has completed 						
 Anaphylactic/Anaphylactoid shock with hypotension and circulatory collapse. 	the review of the IAR and any other relevant safety data (Section 6.5)						

Page **75** of **76**

Appendix C: Dose Modification and Stopping Rules for LAL-CL03 Study

In the absence of an approved grading scale that can be applied to specific patient populations, this protocol will apply the National Cancer Institute Common Toxicity Classification of Adverse Events (NCI CTCAE), version 4.0 or higher. (http://evs.nci.nih.gov/ftp1/CTCAE/CTCAE_4.03_2010-06-14_QuickReference_8.5x11.pdf).

The following stopping rules apply to the decision to pause dosing in individual subjects:

For IARs (refer to the definition in Section 6.5), the following stopping rules will apply:

 Subjects who develop a Grade 3 (severe) or higher IAR must stop treatment until their information is reviewed by the SC. Dosing with alterations to the infusion regimen (e.g., pretreatment and/or slowing the rate of infusion) may resume once the SC and the Sponsor approve. Confirmation may also be sought from regulatory authorities prior to resuming dosing.

Page 76 of 76

2.1 Summary of Amendments

The following updates have been made to the planned analysis:

- Urinalysis and ADA assessments will only be presented in the listings. Summaries will not be presented.
- For specified lab parameters, change from baseline and percent change from baseline will not displayed in spaghetti plots.
- The per protocol analysis set will not be used to summarize results.
- Adverse event will be presented for time periods spanning the entire treatment period. The periods that will be used are 0 to 12 Months, >12 to 24 Months, >24 to 36 Months, >36 to 48 Months, and >48 Months
- Denver II scores will only be presented in a listing.

STATISTICAL ANALYSIS PLAN

An Open Label, Multicenter, Dose Escalation Study To Evaluate The Safety, Tolerability, Efficacy, Pharmacokinetics, and Pharmacodynamics of SBC-102 in Children with Growth Failure Due to Lysosomal Acid Lipase Deficiency

Protocol LAL-CL03

Protocol Number: LAL-CL03

Protocol Version and Date: Amendment 10: 24 January 2014

Amendment 9: 19 March 2013 Amendment 8: 05 February 2013 Amendment 7: 23 October 2012 Amendment 6: 05 April 2012 Amendment 5: 20 September 2011 Amendment 4: 02 June 2011 Amendment 3: 20 May 2011 Amendment 2: 19 April 2011 Amendment 1: 09 February 2011

Original: 10 January 2011

Name of Test Drug: SBC-102 (sebelipase alfa)

Methodology: Open Label, Multicenter, Dose Escalation

Sponsor: Synageva BioPharma Corp.

[name]

Tel: PPD Fax: PPD

Sponsor Representative:

PPD PPD

Synageva BioPharma Corp.

Analysis Plan Date: 07 March 2014

Analysis Plan Version: Final Version 1.1

Confidentiality Statement

The information contained herein is confidential and the proprietary property of Synageva BioPharma Corp. and any unauthorized use or disclosure of such information without the prior written authorization of Synageva BioPharma Corp. is expressly prohibited.

APPROVAL SIGNATURE PAGE

Protocol Title:

An Open Label, Multicenter, Dose Escalation Study To

Evaluate The Safety, Tolerability, Efficacy,

Pharmacokinetics, and Pharmacodynamics of SBC-102 in Children with Growth Failure Due to Lysosomal Acid

Lipase Deficiency.

Sponsor:

Synageva BioPharma Corp.

[name]

Protocol Number:

LAL-CL03

Document Date / Version:

07 March 2014 / Final Version 1.1

PPD

Veristat, Inc. Author:

PPD

Signature:

Veristat, Inc.

[name] ate: 07 Mar 2014

Sponsor Approval

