3.1 Overview of Study Design and Flow Chart

This is an open-label, repeat-dose, dose escalation study of sebelipase alfa in children with growth failure due to LAL Deficiency. Eligible subjects will receive IV infusions of sebelipase alfa for up to 5 years, as described below. All subjects will be evaluated for safety, tolerability, and efficacy. Where feasible, given blood volume thresholds based on subject weight, blood samples will also be collected for analyses of the PK and PD of sebelipase alfa and for an exploratory analysis of potential disease-related biomarkers in this patient population.

All subjects will initiate treatment with sebelipase alfa at a dose of 0.35 mg/kg qw. After receiving 2 infusions at this starting dose, a subject will receive a dose increase to 1 mg/kg qw, contingent upon acceptable safety and tolerability of preceding infusions. A further dose escalation to 3 mg/kg qw may be considered for a subject who has received at least 4 infusions at a dose of 1 mg/kg qw, and meets the criteria for dose escalation defined in Section 3.1.1, contingent upon acceptable safety and tolerability of preceding infusions.

An independent safety committee will oversee safety in this study. The SC will review available safety data for each subject (1) following the first 2 infusions at a dose of 0.35 mg/kg qw to determine the acceptability of escalating the dose to 1 mg/kg qw and (2) following the first 2 infusions at a dose of 1 mg/kg qw to determine the acceptability of continuing treatment at this dose level. In addition, for subjects who are escalated to a dose of 3 mg/kg qw, the SC will review their safety data following the first 2 infusions at a dose of 3 mg/kg qw to determine the acceptability of continuing treatment at this dose level. The remainder of the safety data for all subjects will be reviewed during at least biannual periodic meetings of the SC and on an ad-hoc basis as needed in the event of unanticipated safety findings.

If the SC does not approve a subject's dose escalation from 0.35 mg/kg qw to 1 mg/kg qw, but deems it safe for the subject to continue treatment at the starting dose of 0.35 mg/kg qw, the subject may continue to receive this starting dose. Re-evaluation of dose escalation will be considered after subsequent SC review and discussion with Sponsor.

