7.1.2 Laboratory Test Abnormality

Laboratory test results will be recorded on the laboratory page of the eCRF. Out of range laboratory test values will be reported as AEs (on the AE page of the eCRF) if they are considered to be clinically significant abnormalities by the Investigator and represent a change from the subject's baseline values.

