- If the start date is completely missing, an AE will not be excluded from treatmentemergent AEs unless the stop date/time is before the start of first treatment.

An Overall AE summary table will be presented and will include the number of subjects with:

- All treatment-emergent AEs
- IRRs
- SAEs
- Treatment-emergent AEs related to SBC-102
- Treatment-emergent AEs leading to discontinuation from the study

Summaries of number of events and incidence rates (frequencies and percentages of subjects) of AEs by MedDRA SOC and Preferred Term will be prepared. Such summaries will also be displayed for all AEs by intensity and by relationship to study drug.

Each subject will be counted only once within each level of the summary. If a subject experiences more than one AE within a level, only the AE with the strongest relationship or the maximum intensity, as appropriate, will be included in the summaries of relationship and intensity.

No inferential statistical tests will be performed.

In addition, frequency of AEs, SAEs, and IRRs will be presented for time periods spanning the entire course of treatment with SBC-102: from the start of dosing with SBC-102 in this study to 3 months after the first dose, >3 to 6 months, >6 to 12 months, >12 to 18 months, >18 to 24 months and >24 months.

All AEs will be listed. Separate listings of SAEs, IRRs, AEs leading to study discontinuation, and AEs leading to discontinuation of SBC-102 will also be provided.

As appropriate, a summary of numbers of events and incidence rates (frequencies and percentages or subjects) of IRRs, and AEs leading to withdrawal from the study by SOC and Preferred Term will be prepared for the FAS. No inferential statistical tests will be performed.

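### The SAP update drops every year-1 cut point from the by-period adverse-event table, so start-up and the earliest dose steps are pooled with the rest of the first year (minor)

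*SAP*

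**What the plan says.** Protocol 8.8.1 asks for the frequency of AEs, SAEs and infusion-associated reactions by time since first dose. The first window runs to 3 months, followed by ">3 to 6 months, >6 to 12 months, >12 to 18 months, >18 to 24 months and >24 months". The body of the SAP (Section 10.1, plan dated 07 March 2014) uses the same six windows, beginning from dosing "in this study to 3 months after the first dose, >3 to 6 months".

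The Summary of Amendments at the front of the SAP changes this for adverse events: "The periods that will be used are 0 to 12 Months, >12 to 24 Months, >24 to 36 Months", then >36 to 48 and finally >48 months. It gives no reason, does not say whether the separate SAE and reaction displays change too, and does not name the report it applies to. The list carries no date in the text available.

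Two other parts of the protocol bear on the point:

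- **Dose steps.** Section 3.1 sets the first step: "After receiving 2 infusions at this starting dose, a subject will receive a dose increase to 1 mg/kg qw", subject to safety. A step to 3 mg/kg may follow after at least 4 infusions at 1 mg/kg. Section 3.1.1.2 allows a case-by-case request for up to 5 mg/kg after at least 4 infusions at 3 mg/kg.
- **Reports.** Under Section 12 the first study report "will include all available subject data through 12 months of age or the date of death or early withdrawal". A final report with cumulative data follows study completion.

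**The concern.** The protocol treats the start of each dose level as a period to watch. The Safety Committee reviews each child after the first 2 infusions at 0.35, 1 and 3 mg/kg (Section 3.1), and outpatients are telephoned 24 hours after those infusions. A 0-3 month window in the event table matches that attention. A 0-12 month window does not: an event at the second infusion and one at the fiftieth land in the same cell.

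Safety and tolerability is a secondary objective (Protocol 2.2). What is at stake is whether a reader of the tables can see if events gather around start-up and early escalation or are spread across the first year.

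**Working it through.** No sample size, power or error-rate figure is involved. The check compares window boundaries with the dosing timeline.

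**1. Cut points.**

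| Source | Windows (months from first dose) | Cut points inside year 1 |
|---|---|---|
| Protocol 8.8.1; SAP 10.1 | 0-3, >3-6, >6-12, >12-18, >18-24, >24 | 3 and 6 |
| SAP Summary of Amendments | 0-12, >12-24, >24-36, >36-48, >48 | none |

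The update also drops the 18-month cut point, but it adds detail after 24 months, where the protocol has one open-ended window.

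**2. Earliest dose timeline** (weekly infusions, none missed, each step taken as soon as it is allowed):

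- 0.35 mg/kg: Weeks 0 and 1.
- 1 mg/kg: from Week 2. Four infusions occupy Weeks 2 to 5.
- 3 mg/kg: Week 6 at the earliest. Four infusions occupy Weeks 6 to 9.
- Above 3 mg/kg, up to 5 mg/kg, case by case: Week 10 at the earliest.

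With the SAP's month length of 30.4375 days (Section 7.2), 3 months = 3 × 30.4375 / 7 = 13.04 weeks. Weeks 2, 6 and 10 all come before this. The first exposure to every dose level can therefore fall inside the protocol's first window.

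**3. Share of infusions.** Weeks 0 to 13 give 14 infusions by 3 months. Twelve months = 12 × 30.4375 / 7 = 52.18 weeks, so Weeks 0 to 52 give 53 infusions. 14 / 53 = 26%.

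**4. Which report can show a full first year.** Exposure at 12 months of age = 12 minus age at first dose, in months. It is always below 12. A child first dosed at 8 months, the limit for the Primary Efficacy Analysis Set, contributes 12 − 8 = 4 months. A child first dosed after 12 months of age, which entry up to 24 months allows, contributes no treated time. Only the final report can hold a complete first year.

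**5. Conditional: if the update also governed the report cut at 12 months of age.**

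| Age at first dose | Exposure at cut | Protocol windows reached | Updated windows reached |
|---|---|---|---|
| under 6 months | over 6, under 12 months | 3 | 1 |
| 6 to 8 months | 4 to 6 months | 2 | 1 |

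**The case against.** **The early report may be untouched.** A reader might infer that the report at 12 months of age will show a single window. The documents do not support this. The SAP body of 07 March 2014 keeps the 3- and 6-month cut points and describes treatment for up to 4 years. A >48-month window fits the current 5-year protocol better, which suggests that the update was written for the final analysis. That is inference, since the list is undated, but it argues against the stronger reading. Step 5 of the working is therefore conditional.

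**The loss is narrow.** This stands. SAP 10.1 keeps listings of all AEs, with separate SAE and reaction listings, and SAP 7.1 adds the dosing regimen at the time. The update does not withdraw the optional outputs on reaction frequency and severity over time in Protocol 8.8.1. About 10 children are planned, no formal tests are planned (8.11.1), and Section 8 calls the final analyses supportive. Even so, listings and optional outputs do not replace a prespecified tabulation.

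**A 0-3 month column is not a pure escalation column.** Also correct. Section 3.1.1.2 allows escalation after 3 months, so the split isolates start-up and the earliest possible steps, not all escalation.

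**Other inferences to avoid.** A reader might object that scheduled laboratory work thins out, so yearly windows are unevenly ascertained. Testing is also denser at the start of year 1, so the protocol's own windows share that feature. Nor can a dilution factor be given: the documents state no event rates, and the SAP plans event counts and percentages of children, not risk per infusion. The secondary objective does not itself mention change over time.

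**Conclusion.** The point holds as a minor one. The update removes the 3- and 6-month cut points without a stated reason, and the by-period AE table then pools first doses and the earliest possible dose steps with the rest of year 1. It matters most for the final report.

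The size is structural: two cut points lost, and about a quarter of first-year infusions (14 of 53) no longer separable in that table. This assumes uninterrupted weekly dosing, and the step timing assumes the earliest permitted escalation. Children who escalate later, or not at all, will have fewer steps inside the first 3 months.

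Two matters remain open: whether the update reaches the 12-months-of-age report, and whether it changes the SAE and reaction displays. The mismatch between the amendment list and the older SAP body is not the criticism. The criticism is of the windows chosen going forward, measured against the current protocol.

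**What to change.** In the SAP update, use 0-3, >3-6, >6-12, >12-24, >24-36, >36-48 and >48 months, and apply these windows to AEs, SAEs and IARs/IRRs alike. Show under each window the number of children on treatment at its start. State which report the update governs.

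This keeps the useful yearly windows after year 1 and takes the table from five columns to seven. The cost is SAP wording, two columns and a row of denominators in one table family, with no new data. The downside is small cells in the early windows, which the denominators will make plain.
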